### **9.2 Test of Assumptions**

The continuous variables will be compared using Student's t test (2 groups) or analysis of variance ( $> 2$  groups). If the conditions for applying these tests are not met normality assumption, the Wilcoxon rank sum (2 groups) or Kruskal-Wallis ( $> 2$  groups) non-parametric tests will be used. Comparison within group will be tested by using paired t test. If the normal assumption is violated, the Wilcoxon signed-rank test will be conducted. The category variables will be compared between groups using the Chi-square test if the theoretical total of each class studied is greater than 5. Otherwise Fisher's exact test will be used.

Protocol: GHLIP-2-001

Study Sponsor: Golden Biotechnology Corporation

## 9.3 Primary Endpoint Analysis

The primary efficacy endpoint (percentage change of TG) for assessing the superiority of Antroquinonol (50mg, 100mg, 150mg) to placebo is the percentage change in patients with hyperlipidemia by using analysis of covariance (ANCOVA) model using baseline measurement as covariates (model 1). If the differences in baseline characteristics, such as gender, age, weight etc., are observed, for comparing the effectiveness between the treatment groups and placebo, the model will be performed by multiple linear model (model 2) to adjust characteristics.

Model 1:  $Y_{\text{percentage change of TG} (\%)} = \beta_1 + \beta_2 X_{\text{treatment}} + \beta_3 X_{\text{baseline of TG}}$

Model 2:  $Y_{\text{percentage change of TG} (\%)} = \beta_1 + \beta_2 X_{\text{treatment}} + \beta_3 X_{\text{baseline of TG}} + \beta_4 X_{\text{significant characteristic in baseline}}$

If statistical significance of ANCOVA treatment effect is reached ( $p\text{-value} < 0.05$ ), Bonferroni's method, and two independent t-test (section 7.7) will be performed post hoc analysis for pairwise comparison of percentage change in TG (Antroquinonol 50 mg vs. Placebo, Antroquinonol 100 mg vs. Placebo, Antroquinonol 150 mg vs. Placebo, Antroquinonol 100 mg vs. Antroquinonol 50 mg and Antroquinonol 150 mg vs. Antroquinonol 100 mg).

If the normal assumption is violated for percentage change of TG in any treatments, Kruskal-Wallis test will replace ANCOVA. If statistical significance of Kruskal-Wallis test treatment effect is reached ( $p\text{-value} < 0.05$ ), two independent t-test or Wilcoxon rank-sum test will be performed post hoc analysis for pairwise comparison of percentage change in TG (Antroquinonol 50 mg vs. Placebo, Antroquinonol 100 mg vs. Placebo, Antroquinonol 150 mg vs. Placebo, Antroquinonol 100 mg vs. Antroquinonol 50 mg and Antroquinonol 150 mg vs. Antroquinonol 100 mg).

Protocol: GHLIP-2-001

Study Sponsor: Golden Biotechnology Corporation

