## **7.7 Adjustments for Multiplicity**

For comparison of percentage change in TG of three groups with placebo, 100mg vs. 50 mg, and 150mg vs. 100mg, the post hoc tests will be used to detect which group differ from the rest while statistical significance of ANCOVA or Kruskal-Wallis test. For ANCOVA, the required significance criterion alpha is 0.05 divided by the total number of tests. To correct the multiple testing for primary endpoint, the p-value will be adjusted according to Bonferroni's method to reject the null hypothesis (p-value <0.05/m, m= number of tests). In addition, two independent t-test will also be used for pairwise comparison (p-value=0.05 for all multiple tests). For Kruskal-Wallis test, two independent t-test or Wilcoxon rank-sum test will be used for pairwise comparison (p-value=0.05 for all multiple tests).

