## 9.4 Secondary Endpoint Analyses

Analysis of other secondary efficacy endpoints (TC, HDL-C, LDL-C, and LDL/HDL ratio as well as the effect of Antroquinonol on E/E', baPWV and ABI and HU parameters) will be similar to the primary analysis of the primary endpoint by using ANCOVA model using baseline measurement as covariates, or using Kruskal-Wallis test when normal assumption is violated. Pairwise comparison will use two independent t-test or Wilcoxon rank-sum test, and performed significance level of 0.05 while statistical significance of ANCOVA or Kruskal-Wallis test treatment effect is achieved (Antroquinonol 50 mg vs. Placebo, Antroquinonol 100 mg vs. Placebo, Antroquinonol 150 mg vs. Placebo, Antroquinonol 100 mg vs. Antroquinonol 50 mg and Antroquinonol 150 mg vs. Antroquinonol 100 mg).

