## 9.7 Interpretation and Conclusion

All tests are two-tailed unless otherwise specified and the overall significant level is set to be 0.05. When the number of hypothesis in a test is increased, the Bonferroni correction would be used to test each of the individual tests at a significance level of  $0.05/m$  ( $m$ = number of tests=5, section 9.3). Statistical significance will be demonstrated if the p-value is less than the significance level of test. Regardless of the outcome declared statistically significant, all results could be stated on the Clinical Study Report (CSR).

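### SAP 7.7 allows the five pairwise TG comparisons at 0.05 each, while SAP 9.7 sets 0.05/5; the conflict is clearest after the Kruskal-Wallis switch, whose normality trigger is also undefined

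*SAP*

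**What the plan says.** SAP 9.3 makes ANCOVA with baseline TG (Model 1) the primary analysis. If the treatment effect is significant at 0.05, "Bonferroni's method, and two independent t-test (section 7.7) will be performed post hoc analysis for pairwise comparison of percentage change in TG". Five comparisons are listed: each dose against placebo, 100 against 50 mg, and 150 against 100 mg. SAP 9.3 then adds a switch: "If the normal assumption is violated for percentage change of TG in any treatments, Kruskal-Wallis test will replace ANCOVA". A significant Kruskal-Wallis test is followed by the same five comparisons.

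The thresholds for those comparisons are set in two places.

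- **SAP 7.7, after ANCOVA:** the primary p-value is Bonferroni-adjusted to reject the null hypothesis. The section then adds "In addition, two independent t-test will also be used for pairwise comparison (p-value=0.05 for all multiple tests").
- **SAP 7.7, after Kruskal-Wallis:** "For Kruskal-Wallis test, two independent t-test or Wilcoxon rank-sum test will be used for pairwise comparison (p-value=0.05 for all multiple tests").
- **SAP 9.7:** "All tests are two-tailed unless otherwise specified and the overall significant level is set to be 0.05", and with several hypotheses "the Bonferroni correction would be used to test each of the individual tests at a significance level of" 0.05/m. It gives m = 5, cites section 9.3, and does not limit the rule to one branch.

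On the trigger, SAP 9.2 says only "If the conditions for applying these tests are not met normality assumption", and SAP 9.4 repeats the switch for the secondary endpoints ("or using Kruskal-Wallis test when normal assumption is violated"). Protocol 9.4 reserves it for data that point strongly to a violation. No section names a test or a cut-off.

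**The concern.** A dose with p = 0.03 against placebo succeeds under SAP 7.7's 0.05 rule and fails under SAP 9.7's 0.01 rule. After Kruskal-Wallis no adjusted test is specified in SAP 7.7, so the two sections contradict each other directly. The analyst may also choose between t-test and Wilcoxon. After ANCOVA the text leans towards Bonferroni, but a second set of results at 0.05 sits beside it with no stated role.

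The omnibus test does not settle this. With four arms it protects against a false claim only when all arms are equal. Once one dose works, the gate opens often and the comparisons among the remaining equal arms are tested at full level.

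The switch is the lesser part. The fallback test is pre-specified, but what triggers it is not. The check is on the outcome within each arm rather than on model residuals, and it removes baseline TG from the primary analysis.

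**Working it through.** **Inputs from the documents.** 24 evaluable per arm, assumed reduction 27.5 and SD 40 (protocol 9.2); 1:1:1:1 allocation; omnibus gate at 0.05 and five comparisons (SAP 9.3); two-sided testing (SAP 7.12 and 9.7). **Assumed, not in the documents:** correlation of percentage change with baseline TG between 0 and -0.45; normal percentage change, with lognormal TG as an alternative.

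**Step 1, the plan's own figure.** SAP 9.3 lists 3 + 2 = 5 comparisons, and 0.05/5 = 0.01. This agrees with SAP 9.7. The SAP 7.7 threshold is five times larger.

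**Step 2, error if only 150 mg works.** Three of the five comparisons are then truly null: 50 v placebo, 100 v placebo and 100 v 50. The simple bound on a false claim is 3 x 0.05 = 15%, or 3 x 0.01 = 3%. Simulated with the gate kept (SD 40, 27.5-point effect at 150 mg, normal data):

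| Rule | Any false pairwise claim |
|---|---|
| ANCOVA gate, t-tests at 0.05 counted | about 11% |
| Kruskal-Wallis gate, Wilcoxon at 0.05 | 10-11% |
| Kruskal-Wallis gate, whichever of t-test or Wilcoxon is significant | 12-13% |
| Model 1 contrasts at 0.01 | 2-3% |
| Kruskal-Wallis gate, Wilcoxon at 0.01 | 2-3% |

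With lognormal TG the 0.05 rules give 11-13% (14-15% for whichever is significant). Model 1 at 0.01 gives about 4%, and Wilcoxon at 0.01 about 2%. Counting only dose against placebo, the 0.05 rules give about 8-9% and the 0.01 rules about 1.5-3%.

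**Step 3, error if no dose works.** With the gate, the 0.05 rules give about 4-5% in either branch. Without the gate, five unadjusted t-tests would give 18.6%, so the gate does real work here.

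**Step 4, the trigger.** Suppose a 0.05 test were applied in each arm. With four truly normal arms it would fire in 1 - 0.95^4 = 18.5% of trials; at 0.01 per arm, 1 - 0.99^4 = 3.9%. With assumed lognormal TG the simulated rate runs from 32-38% (Lilliefors at 0.01) to 84-90% (Shapiro-Wilk at 0.05). The unnamed test therefore largely decides which primary analysis is run.

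**Step 5, power for 150 mg v placebo.** The standard error is 40 x sqrt(2/24) = 11.55, and 27.5/11.55 = 2.38. At two-sided 0.05, power is Phi(2.38 - 1.96) = 66% (64% by exact t). At two-sided 0.01 it is Phi(2.38 - 2.58) = 42% (39% by exact t). With the gate and baseline TG in the model, power at 0.01 is about 38-51% over the assumed correlations. Kruskal-Wallis followed by Wilcoxon at 0.01 gives about 33-35%. The loss from switching, both branches at 0.01, ranges from 2 to 17 points with the assumed correlation and distribution.

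**The case against.** The case for leaving the text alone has several parts.

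- **SAP 7.7 itself says Bonferroni decides rejection for the primary endpoint.** This stands for the ANCOVA branch, where the added t-tests can be read as supportive. A reader might infer that 0.05 decides a dose claim after ANCOVA; the documents do not support that. They leave the t-tests unlabelled, and the 11% applies there only if those tests are counted.
- **The primary hypothesis in SAP 9.1 is the four-group null, and the pairwise tests are post hoc.** This also stands. It would be wrong to say that the test of the stated hypothesis runs at 11%; it runs at 4-5%. But SAP 9.3 frames the analysis as superiority of each dose to placebo, and those claims rest on the pairwise tests.
- **The 0.05 wording could mean an overall 0.05.** This is unlikely: it is set against the 0.05/m rule in the same section, and no way of sharing 0.05 is given. Protocol 9.4 waives adjustment for multiple endpoints, not for dose comparisons.
- **The Kruskal-Wallis branch follows the protocol.** This stands. The protocol summary attaches Bonferroni to ANOVA and names no adjustment after Kruskal-Wallis, so only the extra t-tests after ANCOVA depart from it.
- **The switch is pre-specified and both branches hold their level under the global null.** Both are true. A reader might infer that it will usually fire, or that it costs a known amount of power. Neither follows, because the protocol limits it to strong evidence of violation and the documents give no baseline correlation.

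**Conclusion.** The plan is wrong as written on the pairwise threshold: 0.05 in SAP 7.7 against 0.01 in SAP 9.7 for the same five comparisons. The contradiction is direct after Kruskal-Wallis. After ANCOVA it is an ambiguity about the role of the extra t-tests. If the 0.05 tests count and only 150 mg works, about one trial in nine makes a false pairwise claim, against about 2-4% at 0.01. If no dose works, error stays near 5%. These error rates rest on 24 per arm and SD 40, and change little over the correlations and distributions tried.

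The undefined normality trigger is a real but secondary gap. How often it would fire and what power it would cost depend on assumptions the documents do not supply.

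**What to change.** **(a) Thresholds.** In SAP 7.7 and 9.3, apply 0.05/5 to the five primary comparisons in both branches, keep the omnibus gate, and name one pairwise method per branch. Delete the unadjusted 0.05 comparisons, or label them supportive and state that no claim rests on them.

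**(b) Preferably, remove the switch.** Keep Model 1 as primary whatever the normality check shows, with Kruskal-Wallis/Wilcoxon or rank ANCOVA on baseline TG as a sensitivity analysis. Then align SAP 9.2 and SAP 9.4 (all secondary endpoints, not only the lipids), make Model 2 supportive, and align the protocol summary and protocol 9.4.

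**(c) Record it.** In SAP 12, list the changes made. If the unadjusted t-tests after ANCOVA are kept as supportive, note that they depart from the protocol's Bonferroni wording.

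**Cost.** Text edits, minor programming and a protocol amendment under protocol 13.5; the percentage-change endpoint is unchanged. Compared with counting the 0.05 t-tests after ANCOVA, power for 150 mg v placebo falls by about 5-9 points if effects are graded by dose, or about 11-15 points if only 150 mg works. Compared with Kruskal-Wallis/Wilcoxon at 0.05, Model 1 at 0.01 ranges from about 12 points lower to 5 points higher. If only (a) is adopted, the Kruskal-Wallis branch has about 33-35% power at 0.01. The SAP should state that power at 0.01 under Model 1 is about 38-51% at SD 40 with normal data. Even the unadjusted 64-66% is below the planned 90%, but that is a separate sample-size matter.

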## 9.4 Secondary Endpoint Analyses

Analysis of other secondary efficacy endpoints (TC, HDL-C, LDL-C, and LDL/HDL ratio as well as the effect of Antroquinonol on E/E', baPWV and ABI and HU parameters) will be similar to the primary analysis of the primary endpoint by using ANCOVA model using baseline measurement as covariates, or using Kruskal-Wallis test when normal assumption is violated. Pairwise comparison will use two independent t-test or Wilcoxon rank-sum test, and performed significance level of 0.05 while statistical significance of ANCOVA or Kruskal-Wallis test treatment effect is achieved (Antroquinonol 50 mg vs. Placebo, Antroquinonol 100 mg vs. Placebo, Antroquinonol 150 mg vs. Placebo, Antroquinonol 100 mg vs. Antroquinonol 50 mg and Antroquinonol 150 mg vs. Antroquinonol 100 mg).

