9.2. Sample Size Considerations

The primary efficacy endpoint in this trial is “to compare the percentage change of triglyceride (TG) from baseline following a 12-week regimen of Antroquinonol versus placebo.” The objective of this trial is to assess the efficacy of the study treatment compared with control treatment. According to the literature review (FDA statistical reviews of Fibrate), the TG reduction percentage change of Fibrate from baseline to last visit was 36.6% for subjects who were treated with the study treatment, and 0.7% increased for the control treatment. According to prior published clinical reference, it is assumed that the mean TG percentage reduction is 27.5% and standard deviation is 40. The evaluable patient number should be at least 24 patients for each group under one-sided significance level 0.025 and power 90%. Considering a 20% drop-out rate, a sample size of 30 patients should be enrolled to each group, and a total of 120 patients will be recruited into this study. The sample size calculation was derived using PASS 2008.

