## **5 SAMPLE SIZE DETERMINATION**

The sample size estimation of this study is using two-sample T-test under one-sided significance level 0.025, power 90%. Based on the Davidson's study, the TG reduction percentage change of 130 mg Fenoribrate from baseline to last visit was 36.6% for subjects who were treated with the study treatment, and the standard deviation was 2.4% and 5.3% for the study treatment and the control treatment. Assuming a drop-out rate of 20%, a sample size of 120 patients (30 patients per arm) were required to provide 96 evaluable patients (24 patients for each group) which indicates an achievement of 80% completion rate.

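### On the ANCOVA route, SAP 9.4 draws the secondary dose-versus-placebo conclusions from two-sample tests without the baseline term, which costs precision and lets them disagree with the model that licensed them

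*SAP*

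**What the plan says.** SAP 9.4 covers eight secondary endpoints: TC, HDL-C, LDL-C, LDL/HDL ratio, E/E', baPWV, ABI and liver HU. Each is analysed "by using ANCOVA model using baseline measurement as covariates", or by Kruskal-Wallis if normality fails. If the overall treatment effect is significant, five pairs are compared: each dose with placebo, 100 mg with 50 mg, and 150 mg with 100 mg. For these, "Pairwise comparison will use two independent t-test or Wilcoxon rank-sum test, and performed significance level of 0.05".

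For TG, SAP 9.3 fits Model 1 (treatment plus baseline TG). After a significant treatment effect, "Bonferroni's method, and two independent t-test (section 7.7) will be performed post hoc analysis for pairwise comparison" on the same five pairs. SAP 7.7 ties the Bonferroni threshold to ANCOVA and then adds that "two independent t-test will also be used for pairwise comparison", each at 0.05. SAP 9.7 sets the number of Bonferroni tests at five.

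SAP 7.5 and 9.3 present the baseline-adjusted model as the means of comparing the doses with placebo. Protocol 9.4 says only that the secondary analyses will resemble the primary one.

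**The concern.** The secondary objective is the effect of Antroquinonol against placebo, so the pairwise comparisons carry the answer. The overall ANCOVA says only that some arm differs. SAP 9.4 includes baseline in the overall test and leaves it out of the comparisons from which conclusions are drawn. They also use the variance of two arms rather than four.

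Two things follow on the ANCOVA route. If change is correlated with baseline, every dose effect is estimated less precisely than the fitted model allows. And because gate and follow-up are different analyses, a significant ANCOVA may be followed by pairwise tests that do not bear it out, with no rule for reading the conflict. Chance baseline imbalance, which is likely to matter at about 24 evaluable patients per arm, stays in the estimate. For HU the arms are smaller still, because Protocol 7.5.1 rescans only patients with fatty liver.

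**Working it through.** **Inputs.** Protocol 9.2: "it is assumed that the mean TG percentage reduction is 27.5% and standard deviation is 40", with 24 evaluable patients per group. SAP 5 names a two-sample t-test at one-sided 0.025, equivalent in size to the two-sided 0.05 used at analysis. Neither document gives r or a planning SD for any secondary endpoint. So r is an assumption shown over a range, and the TG effect is borrowed for illustration.

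**The plan's own figure.** With an effect of 27.5 and SD 40, n per group = 2 × (1.960 + 1.282)² × (40/27.5)² = 44.5, so 45 by the normal approximation and 46 by the exact t calculation. The stated 24 is not reproduced. At 24 per group the standardised effect is 27.5/40 = 0.6875, and two-sample t-test power (46 df) is 64.5%, not 90%. That is a separate matter, and the present point does not depend on it.

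**Variance penalty.** Let baseline and Day 85 have common variance σ² and correlation r.
- Variance of change: 2σ²(1 − r).
- Residual variance after adjusting for baseline: σ²(1 − r²).
- Ratio: 2(1 − r)/(1 − r²) = 2/(1 + r).

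Power for the ANCOVA contrast uses a standardised effect of 0.6875 × √(2/(1 + r)) with 96 − 5 = 91 df.

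| r | 2/(1+r) | Unadjusted n per arm for equal precision (24 × ratio) | t-test power | ANCOVA contrast power |
|---|---|---|---|---|
| 0.4 | 1.43 | 34.3 | 64.5% | 80.4% |
| 0.6 | 1.25 | 30.0 | 64.5% | 75.0% |
| 0.8 | 1.11 | 26.7 | 64.5% | 70.0% |
| 0.9 | 1.05 | 25.3 | 64.5% | 67.6% |

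At r = 0.95 the penalty is 3%.

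**Cross-check.** In terms of the correlation ρ between change and baseline, the penalty is 1/(1 − ρ²). With equal variances ρ² = (1 − r)/2, so r = 0.4, 0.6 and 0.8 correspond to |ρ| = 0.55, 0.45 and 0.32 and give the same ratios. At ρ = 0 nothing is lost.

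**Percentage change.** The lipid endpoints are percentage changes. With an assumed baseline coefficient of variation of 10% to 30%, the ratios are 1.44–1.46, 1.26–1.28 and 1.11–1.13 at r = 0.4, 0.6 and 0.8, so the result does not hinge on absolute change.

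**Disagreement.** In simulated trials with four arms of 24 and the illustrative effect in every dose, the t-test and the ANCOVA contrast gave different verdicts at 0.05 on a given dose-placebo pair in about 20%, 16% and 11% of trials at r = 0.4, 0.6 and 0.8. Among trials that passed the ANCOVA gate the figures were about 20%, 14% and 9%. Two-arm against four-arm variance pooling, with no baseline term in either test, alone produces about 4–5%.

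**The case against.** Several counter-arguments stand.

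- **Validity.** A reader might infer that the pairwise tests are biased. Randomisation makes the unadjusted comparison unbiased, and chance imbalance is already reflected in its standard error. The loss is one of efficiency, on secondary endpoints in a Phase II trial.
- **Kruskal-Wallis route.** No adjusted model exists there, so Wilcoxon follow-up is coherent. The criticism does not reach it, and a remedy offering only LS-means would leave that route without a pairwise method.
- **TG.** A reader might infer that the primary conclusion rests on unadjusted t-tests. SAP 7.7 links Bonferroni to ANCOVA and adds the t-tests beside it. What is missing is a statement that the Bonferroni comparisons are Model 1 contrasts and that they govern.
- **Size.** It is tempting to read the power gap as the loss on each secondary endpoint. The documents give no r and no planning SD for these endpoints, and HU will have fewer patients. Nor do the figures describe the governing TG test, whose threshold is 0.05/5 = 0.01.
- **Cause.** Part of the disagreement comes from variance pooling rather than the dropped covariate.
- **Cost.** Pooling four arms assumes similar variances. SAP 5 prints SDs of 2.4% (treatment) and 5.3% (control). With those, a dose-placebo difference has variance proportional to 5.3² + 2.4² = 33.85. Four-arm pooling assumes 2 × (5.3² + 3 × 2.4²)/4 = 22.69, so the standard error is too small by a factor of √(33.85/22.69) = 1.22. In simulation without an effect, the pooled contrast rejects in about 11% of trials at nominal 5%, the two-arm t-test in about 5%. Protocol 9.2 assumes one SD of 40, so unequal variances are not established, but the risk needs a check.

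None of this supplies a reason to fit the baseline term and then leave it out of the comparisons.

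**Conclusion.** The point holds for the ANCOVA route of SAP 9.4 and for all eight secondary endpoints. The planned pairwise tests are valid but less precise than contrasts from the model already fitted, and they can disagree with it. With equal baseline and Day 85 variances the variance penalty runs from 43% at r = 0.4 to 5% at r = 0.9, and it vanishes as change becomes uncorrelated with baseline. The power difference, from about 16 points down to about 3, rests on the TG planning effect and 24 per arm and is illustrative only.

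For TG the fault is narrower: the SAP does not say which pairwise result governs. The documents do not support calling the secondary tests invalid, faulting the Wilcoxon follow-up after Kruskal-Wallis, or saying that the primary conclusion is compromised on this ground. Changing the significance level would not address the point, because the tests would still lack the baseline term.

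**What to change.** In SAP 9.4, replace the pairwise sentence with:

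*When ANCOVA is used, pairwise comparisons are LS-mean differences with 95% CI from that same ANCOVA (four-level treatment factor, baseline value as covariate); when Kruskal-Wallis replaces ANCOVA, pairwise comparisons use the Wilcoxon rank-sum test.*

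In SAP 7.7 and 9.3, state that on the ANCOVA route the Bonferroni-adjusted TG comparisons are Model 1 contrasts and that these govern. Delete the additional two-sample t-tests on that route or label them supportive.

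Add a check of residual variance across arms, with a heteroscedasticity-robust or unequal-variance standard error if similarity fails.

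The cost is SAP wording, one LS-means statement per endpoint in the SAS analysis already planned, and the variance check. No new data are needed. The one small downside is the reliance on pooled variance, which the overall ANCOVA already assumes.
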